8.4. Definition of Clinical Laboratory Abnormalities and Other Abnormal Assessments as AE/SAE

Abnormal laboratory findings (hematology, coagulation, chemistry, and urinalysis) or other abnormal assessments (ECG, vital signs) per se are not reported as AEs. However, those abnormal findings that are deemed clinically significant or are associated with signs and/or symptoms must be recorded as AEs if they meet the definition of an AE (or recorded as an SAE if they meet the criteria of being serious) as previously described. Clinically significant abnormal laboratory or other abnormal findings that are detected after consent or that are present at baseline and worsen after consent are included as AEs (and SAEs if serious).

The investigator should exercise medical and scientific judgment in deciding whether an abnormal laboratory finding, or other abnormal assessment is clinically significant. Usually, the abnormality should be associated with a clinically evident sign or symptom or be likely to result in an evident sign or symptom in the near term, to be considered clinically significant.

A clinically significant laboratory abnormality in the absence of clinical symptoms may jeopardize the subject and may require intervention to prevent immediate consequences. For example, a markedly low serum glucose concentration may not be accompanied by coma or convulsions, yet be of a magnitude to require glucose administration to prevent such sequelae.

8.5. Assessment of Adverse Events

8.5.1. Assessment of Adverse Event/Serious Adverse Event Severity

The severity, or intensity, of an AE refers to the extent to which an AE affects the subject’s daily activities. Severity will be graded according to the World Health Organization (WHO) Toxicity Grading Scale, March 2020 or later. If an AE is not specified within the WHO Toxicity Grading Scale, then the AE will be graded according to the following definitions:

Grade	Severity	Description
1	Mild	Transient or mild discomfort; no limitation in activity; no medical intervention or therapy required. The subject may be aware of the sign or symptom but tolerates it reasonably well.
2	Moderate	Mild to moderate limitation in activity; no or minimal medical intervention or therapy required.
3	Severe*	Marked limitation in activity; medical intervention or therapy required; hospitalizations possible.
4	Life-Threatening	The subject is at risk of death due to the AE as it occurred. This does not refer to an AE that hypothetically might have caused death if it were more severe.
5	Death	Any AE where the outcome is death.

Abbreviation: AE=adverse event.

*Note that the term “severe” is a measure of intensity and that a severe AE is not necessarily serious.

Changes in the severity of an AE should be documented to allow an assessment of the duration of the event at each level of intensity to be performed. AEs characterized as intermittent do not require documentation of onset and duration of each episode. When the intensity of an AE changes more than once a day, the maximum severity for the event should be listed. If the intensity changes over a number of days, these changes should be recorded separately (ie, as having distinct onset dates).

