8.1. Definition of Adverse Event

Adverse events are any untoward medical occurrence in a subject enrolled into this study, including side effects, injury, toxicity, sensitivity reaction, intercurrent illnesses, clinically significant physical exam signs, or sudden death, whether or not it is considered related to the study treatment. Subjects will be instructed to contact the investigator at any time after informed consent if any symptoms develop. Subjects will be instructed to report all AEs to the investigator. All AEs must be appropriately documented in the subject's original source documents and on the eCRFs. Investigators should report the diagnosis rather than list symptoms, whenever possible.

A treatment-emergent AE (TEAE) is defined as any event not present before first administration of study treatment or any event already present that worsens in either intensity or frequency after first administration of study treatment.

Adverse events resulting from concurrent illnesses, reactions to concurrent illnesses, reactions to concurrent medications, or progression of disease states must also be reported within the established time frames.

An AE does not include the following:

- Elective medical or surgical procedures planned prior to the start of study treatment (eg, hip replacement surgery) that did not result from a worsening of a previous condition (ie, prior to signing informed consent). *Note:* Any serious procedural complication or hospital-emergent conditions (eg, nosocomial infection) would be reported as an SAE.
- Any medical condition or clinically significant laboratory abnormality that has an onset date before the consent form is signed, and that is not related to a protocol-associated procedure, is not an AE. Such conditions are considered to be pre-existing and should be documented on the medical history eCRF. A pre-existing condition should be reported as an AE only if its frequency, intensity, or symptoms worsen during the course of the study.
- Situations where an untoward medical occurrence has not occurred (eg, hospitalization for study treatment administration per institutional guidelines, elective surgery, social and/or convenience admissions).

- Overdose without adverse event.
- Disease progression within expected parameters for the study population is not considered an AE. See [Section 8.3](#) for Protocol Specific Disease Progression Adverse Event and Serious Adverse Event Reporting Requirements.

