9.3.6. Safety Analyses

9.3.6.1. Safety

Safety will be assessed by the occurrence of TEAEs, treatment-emergent SAEs, and treatment-emergent clinically significant abnormalities in clinical and laboratory values. AEs will be coded to system organ class and preferred term using the MedDRA Version 22.0 or later and summarized as counts of events and proportions of subjects experiencing a given type of event, by treatment group.

Summaries by severity, relationship to the study intervention, action taken with respect to study intervention, and outcome of all TEAEs will also be provided, by treatment group.

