4.4. Adverse Events

AEs are collected regardless of cause or relationship that occur after signing of informed consent through end of study visit. Treatment emergent adverse events are those AEs with a start date on or after the date of first administration of investigational product. All AEs will be listed with a flag to indicate if an AE is treatment emergent.

In addition, all serious adverse events (SAEs) and AEs leading to discontinuation of study medication will be listed, with a flag to indicate if an AE is treatment emergent.

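### Under the SAP's start-date rule, an adverse event present before dosing that eases afterwards is flagged treatment-emergent, contrary to Protocol 8.1

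*Protocol*

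**What the plan says.** Protocol 8.5.1 sets the recording rule: "If the intensity changes over a number of days, these changes should be recorded separately (ie, as having distinct onset dates". Two exceptions limit it: "When the intensity of an AE changes more than once a day, the maximum severity for the event should be listed", and "AEs characterized as intermittent do not require documentation of onset and duration of each episode". The stated purpose is to measure time spent at each grade: "Changes in the severity of an AE should be documented to allow an assessment of the duration of the event at each level of intensity".

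The documents define treatment emergence in two ways. Protocol 8.1 includes an event that was absent before the first dose, or "any event already present that worsens in either intensity or frequency after first administration of study treatment". SAP 4.4 uses the date alone: "Treatment emergent adverse events are those AEs with a start date on or after the date of first administration of investigational product". The flag applies to every listed event: "All AEs will be listed with a flag to indicate if an AE is treatment emergent". The same section repeats the flag for the SAE listing and for the listing of AEs that led to stopping study medication.

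On output, Protocol 9.3.6.1 has AEs "summarized as counts of events and proportions of subjects experiencing a given type of event, by treatment group". SAP 3.1 plans listings and no formal analysis, because the trial was halted after 5 participants (SAP 1). Both documents collect AEs from consent (Protocol 8.7.1, SAP 4.4), and screening may start up to 21 days before baseline (Protocol Appendix 1, footnote 1). Events that begin before the first dose are therefore in the data.

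**The concern.** The recording rule and the flag do not fit together. A start date can stand in for emergence only if a post-dose start date means that something new or worse has happened. Protocol 8.5.1 breaks that link, because a fall in grade also produces a new onset date. SAP 4.4 has no condition that separates the two directions, and neither document says how the records of one event are tied together.

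Occurrence of treatment-emergent AEs is part of the first-listed primary outcome (Protocol 2). With 5 subjects and listings only, the flag on each line is the treatment-emergence result that a reader of the synoptic report will see. A wrong flag marks an event that was already resolving as one that arose on treatment.

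**Working it through.** The plan gives no figure on this point. Its one safety calculation (Protocol 9.1) is not an input and is not affected. It reproduces: 1 − (1 − 0.052)^30 = 0.7985, and 0.0522 in place of 0.052 gives 0.800, so the stated 80% holds to the rounding of 5.2%.

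The check applies the three rules to assumed event courses. These are illustrations, not trial data. Day 0 is the first dose.

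- **Records (Protocol 8.5.1):** take the highest grade on each day, and open a new record whenever it differs from the previous one.
- **SAP flag (SAP 4.4):** a record is flagged if its onset day is 0 or later. This takes the onset date of a record as the start date of an AE.
- **Protocol status (Protocol 8.1, intensity only):** the event is treatment-emergent, once, if it has no pre-dose record, or if its highest post-dose grade exceeds its last pre-dose grade.

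| Course (day: grade) | Records | Flagged by SAP 4.4 | Treatment-emergent events by Protocol 8.1 |
|---|---|---|---|
| Pre-dose, eases (−5: 2; 3: 1) | 2 | 1 | 0 |
| Pre-dose, worsens (−5: 1; 3: 2) | 2 | 1 | 1 |
| Pre-dose, worsens then eases (−5: 1; 3: 2; 10: 1) | 3 | 2 | 1 |
| Pre-dose, unchanged (−5: 2) | 1 | 0 | 0 |
| Post-dose, 1-2-3-2-1 (days 2, 4, 6, 9, 12) | 5 | 5 | 1 |
| Post-dose, 1-3-1 within day 2 | 1 | 1 | 1 |

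The first row is the contradiction: one flagged record and no treatment-emergent event. The second row shows that the start-date rule works for worsening, but only because the split supplies a new date. Rows one and two look identical to SAP 4.4, with one pre-dose record and one post-dose record each. Only a comparison with the earlier grade of the same event separates them. In the fifth row every flag is right, because the event is new after dosing, but one event occupies five lines.

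Frequency needs separate treatment. An intermittent AE need not have an onset per episode, so one that began before dosing and becomes more frequent may keep its pre-dose start date. SAP 4.4 would then leave it unflagged, although Protocol 8.1 includes it. A repair that compares grades alone would not reach this case.

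On how often the first row could arise, the documents give figures for only one source, the screening lumbar puncture. Protocol 7.2.2 cites fewer than 2.6% with a post-puncture headache, and one patient in over 1,000 with a headache beyond 5 days, in a memory-clinic cohort. Assume that these rates carry over, with one puncture for each of 5 subjects:

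- any headache: 1 − (1 − 0.026)^5 = 0.123, so at most about 12%;
- a headache beyond 5 days: 1 − (1 − 0.001)^5 = 0.005, so at most about 0.5%.

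The headache must also still be present at the first dose and then ease by a grade. Other pre-dose AEs could follow the same path, but the documents give no rate for them.

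**The case against.** The strongest reply is that Protocol 8.5.1 speaks of one event throughout. Its purpose is duration at each intensity, and Protocol 8.6.3 distinguishes a sequela from the same event at a lower grade. On that reading, the separate records are parts of one AE with one start date, and the eCRF may link them. This stands in part. That each record becomes a new AE is an inference, and the documents do not show how the eCRF is built. But 8.5.1 gives the parts distinct onset dates, and SAP 4.4 does not say that the first of them is the start date to use. If it were, a pre-dose event that worsened would go unflagged, which also contradicts Protocol 8.1. Either reading needs a rule that the SAP lacks.

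A second reply is that Protocol 8.1 already excludes the easing event. It does, and the fault lies in SAP 4.4 rather than in the recording rule alone. However, Protocol 9.3.1 leaves the details of the analyses to the SAP, so the SAP's definition is the one that would be programmed.

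A reader might go further and infer that every change of intensity adds an event and that AE totals are inflated. The documents do not support this. Same-day changes collapse to one entry, and intermittent events need no onset per episode. Repeated records do not by themselves change the proportion of subjects affected. The event totals of Protocol 9.3.6.1 are not among the SAP's outputs, and no average number of grade changes per AE is given from which to size an inflation.

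**Conclusion.** The point holds for the flag. Protocol 8.5.1 and SAP 4.4 together mark as treatment-emergent a pre-dose event that eases over days after dosing, and Protocol 8.1 excludes it. This follows from the text, on the assumption that the onset date of a severity record is used as an AE start date. The effect is one wrongly flagged line for each such record.

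Two stronger readings should be resisted. A reader might infer that one false flag moves the share of subjects with a treatment-emergent AE by 1/5 = 20%. That is so only if the subject has no other such event through Week 32, and the SAP reports no proportions. A reader might also infer that, because lumbar puncture is scheduled at Screening, procedure-related AEs will commonly be ongoing at first dose. The low rates that the Protocol cites, and a screening window of up to 21 days, do not support that; such events are possible, no more.

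The problem is therefore a narrow mismatch of definitions. It is still worth correcting, because it touches a primary safety outcome and the repair is small.

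**What to change.** Replace the definition in SAP 4.4 with that of Protocol 8.1, applied to the event rather than the record. Adding a worsening clause to the present text is not enough, because an easing record would still pass the start-date test. The revised section should say three things:

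- consecutive severity records of one event are linked;
- an event with no record before the first dose is treatment-emergent;
- a continuation of a pre-dose event is flagged only if its intensity or frequency is worse than its last pre-dose state.

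Keeping both intensity and frequency matters, since a test on grade alone would create a new conflict with Protocol 8.1. The same flag should be carried into the SAE and discontinuation listings.

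If the event totals of Protocol 9.3.6.1 are ever produced, count each linked event once, at its maximum post-dose severity. No current output needs this.

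The cost is a short change to SAP 4.4 and one linking variable, or a manual link, which is enough for 5 subjects. The downside is a small amount of extra programming or manual review, including a judgement on frequency for intermittent events.

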8.5.2. Assessment of Adverse Event/Serious Adverse Event Causality

The relationship or association of the study treatment in causing or contributing to the AE/SAE will be characterized by the investigator using the following classification and criteria:

Relationship to Study Treatment	Comment
Related	There is reasonable possibility that the event may have been caused by study treatment (eg; confirmation by positive rechallenge test).
Not Related	The event can be readily explained by the subject's underlying medical condition, concomitant therapy, or other causes, and therefore, the investigator believes no relationship exists between the event and study treatment.

The investigator should assess causality by answering either “related” or “not related” to the question “Is there a reasonable possibility that the event may have been caused by the study treatment?” The following factors may be used in consideration of causality assessment:

- Challenge/rechallenge: Did the event abate after study treatment was reduced or interrupted? Did the event reappear after study treatment was reintroduced?
- Temporal relationship and time to onset plausibility
- Confounding risk factors
- Amount and duration of study treatment exposure
- Concomitant medications

8.6. Recording of Adverse Events

8.6.1. Eliciting and Documenting the Adverse Events

At every study visit, subjects will be asked a standard nonleading question to elicit any medically related changes in their well-being. They will also be asked if they have been hospitalized, had any accidents (eg, falls), used any new medications, or changed concomitant medication regimens (prescription drugs, herbal products, vitamins, minerals, vaccines, topical medications, and over-the-counter medications).

Laboratory test values or investigational findings (eg, findings on ECGs, imaging, or examination) outside the normal reference range that meet any of the following criteria should be reported as an AE:

- Is confirmed and the investigator considers it clinically significant

- Requires a subject to discontinue study drug
- Requires a subject to receive treatment

Abnormal laboratory test values or investigational findings reported as AEs or SAEs should be followed until recovered/resolved, until stable, subject withdrawal of consent, lost to follow-up, or death, whichever comes first.

8.6.2. Recording the Action Taken with Investigational Products in Response to Adverse Events/Serious Adverse Events

Should the investigator need to alter the administration of the investigational product from the procedure described in the protocol in response to an AE/SAE, then the action taken will be recorded on the AE eCRF page as one of the following options:

- Dose reduced
- Dose interrupted
- Dose withdrawn
- Not applicable
- Unknown

8.6.3. Recording the Outcome and Follow-Up of Subjects Reporting an Adverse Event/Serious Adverse Event

Outcome of an AE/SAE will be recorded on the AE eCRF as follows:

- Recovered/Resolved
- Recovered/Resolved with Sequelae (with sequelae being a condition that is the consequence of the reported event, and not the event in a lower grade/ severity)
- Not Recovered/Not Resolved
- Fatal
- Unknown (or subject lost to follow-up after 4 attempts to contact over a period of 30 days since last information has been received).

8.7. Reporting Adverse Events

8.7.1. Adverse Event and Serious Adverse Event Reporting

All AEs and SAEs must be recorded and reported, regardless of cause or relationship, that occur after the subject signs informed consent through the end of study (EOS) visit. After this period, Alector should be notified if the investigator becomes aware of any SAE that is believed to be related to prior study drug treatment. Alector will follow any unresolved AEs and/or SAEs through satisfactory clinical resolution. Additionally, SAEs considered related to study treatment that occur at any time should be reported to Alector by the investigator.

In the event of any SAE reported or observed during the study, the investigational site is required to complete the AE eCRF within the EDC system, indicating the AE is serious, within 24 hours

of becoming aware of the event or aware of new information relating to the event. In the event that the EDC system is not available, a paper SAE Report Form should be used and emailed to [contact], according to the instructions provided in the Study-Specific Regulatory Binder.

SAE information to be collected includes the following:

- Event term
- Date of onset of event
- Investigator-specified assessment of severity and relationship to study drug
- Date of resolution of the event
- Seriousness
- All applicable seriousness criteria
- Any required treatment or evaluations
- Event outcome

[figure not shown]
The Medical Dictionary for Regulatory Activities (MedDRA) version 23.0 or later will be used by Alector to code all AEs.

If additional visits are required before EOS, the subject will be asked to return to the investigational site for further follow-up. As additional information becomes available, such as hospital discharge notes and subject medical records, the investigator will be notified and provided with all relevant information. It is the investigator's responsibility to report all SAEs to Alector (covered in this section), and it is Alector's responsibility to ensure that all safety reporting obligations are carried out in compliance with current legislation for expedited reporting of SAEs (including SUSARs).

8.8. Safety Monitoring

Safety will be continuously reviewed by a Medical Monitor in consultation with the study investigators. Adverse events will be reported to the Medical Monitor from the study EDC system at regular intervals throughout the study, and in real time when SAEs occur or when questions arise. The Medical Monitor will have the authority to recommend study discontinuation or modification based on medical concerns, including AE or SAE profiles.

For medical emergencies, contact:

Study Medical Monitor
[name] 

The Medical Monitor will review AE reports, compiled by Data Management, as described in the Safety Monitoring Plan. The Medical Monitor will review blinded study data on enrollment, abnormal laboratory results and protocol deviations. These reports will collectively be known as the Medical Monitoring Report.

Alector will be responsible for notifying the applicable regulatory agencies of any unexpected fatal or life-threatening suspected adverse reaction as soon as possible, but in no case later than 7 calendar days after the sponsor's initial receipt of the information. In addition, Alector must notify the applicable regulatory agencies and all participating investigators in an Investigational New Drug safety report of potential serious risks, from clinical trials or any other source, as soon as possible, but in no case later than 15 calendar days after Alector determines that the information qualifies for reporting.

8.9. Follow-Up of AEs and SAEs

All AEs and SAEs that are deemed related to the investigational product must be followed until resolution, until the condition stabilizes, until the event is otherwise explained, or until the subject dies or is lost to follow-up. The investigator is responsible for ensuring that follow-up includes any supplemental investigations that may be indicated to elucidate as completely as practical the nature and/or causality of the AE/SAE. This may include additional laboratory tests or investigations, histopathological examinations, or consultation with other health care professionals.

Alector may request that the investigator perform or arrange for the conduct of supplemental measurements and/or evaluations. If a subject dies during participation in the study or during a recognized follow-up period, the sponsor should be provided with a copy of any post-mortem findings, including histopathology.

